### Sample size

Calculations based on estimated sample size of 1270, and event rate of 50% are shown below. (8) [<https://www.bmj.com/content/368/bmj.m441>] (Excel spreadsheet of table below available)

Binary outcomes		
Figure 1	Margin of error $\leq 0.05$	
Criteria iii in pms	Outcome proportion ->	0.5
	Total n needed	384.16
Figure 2	Mean absolute prediction error (MAPE) at 0.05 in predicted probabilities when applied to other targeted individuals	
	number of candidate variables ->	18
	Total n needed	1013.2
Figure 3	Target shrinkage of $\leq 10\%$ (i.e. shrinkage factor = .9), Rsquared CS (proportion of variation explained) at least .1	
Criteria i in pms	Total n needed	716.234
	See Fig 4 for notes: Rsq often .1-.2 for binary for medical; use .5 for direct/explanatory	
Figure 5	n participants required to ensure expected optimism of $\leq 0.05$ in the apparent Rsq	
Criteria ii in pms	Anticipated Rsq	0.2
	Ln L null	-693.15
	Max Rsq (depends on proportion)	0.75

	n Outcome	500
	n total sample size (arbitrary)	1000
	Shrinkage factor corresponding to optimism of $\leq 0.05$ in $R^2$	0.84211
	Total n needed	420.427

Estimate the overall outcome proportion with sufficient precision ( $\leq 0.05$ )	384.16
Target a small mean absolute prediction error (0.05)	1013.2
Target a shrinkage factor of 0.9	716.234
Target small optimism of 0.05 in the apparent $R^2$ Nagelkerke	420.427

Data will be analyzed using R (version 4.0.3). Any statistical tests will be two-sided, with significance levels of 0.05.

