### **Model building**

Correlations amongst candidate predictors will be explored to avoid risks of collinearity (for example, between dexamethasone use and type of intraoperative anesthesia). Amongst multiple highly correlated predictors, only one will be selected for the modeling based on clinical reasoning (e.g. one variable is more easily collected, less missing values, etc.). Additionally, potential multicollinearity within the final model will be diagnosed using variance inflation factors (VIF) of the predictors, with any values exceeding 4 warranting further investigation.

Multivariable logistic regression will be the statistical method used to construct a prediction model, with the above outlined imputation procedure applied to the data prior to modelling. The prediction model will contain the complete variable set as predictors (as outlined in the Candidate Predictors section). “Age”, the only continuous predictor to be included in the model, will be modelled with a natural cubic spline (with 3 interior knots).

In addition, an exploratory prediction model will be created where a natural cubic spline (with 3 interior knots) will also be fitted for an additional predictor of “Tourniquet duration”. This serves as an exploration of whether tourniquet duration plays a predictive role. However, this exploratory model could only be used postoperatively, when this information becomes available. Future database with information on predicted tourniquet duration would be needed for model update to minimize bias if this predictor were to be applied preoperatively. The primary and exploratory models will then be compared in terms of predictive performance and a likelihood ratio test will also be conducted to assess differences in goodness-of-fit.

To assess the performance of the predictive models, we will proceed with a bootstrap validation approach with 100 repetitions. At each repetition, the data will be sampled with replacement to form a bootstrap sample (with sample size equivalent to the original dataset). Multiple imputation will then be conducted on the bootstrap sample prior to modelling (using the same procedure outlined in the above “Missing values” section). After the pooled bootstrap model is created for the given bootstrap sample, performance measures (as discussed below) will be pooled across the 10 multiply imputed datasets of (1) the bootstrap sample and (2) the original

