dataset. These will individually form estimates of the “training” and “test” performance, permitting us to compute the optimism of the pooled bootstrap model.

This process will be repeated for each of the repetitions, and optimism estimates will be averaged over the 100 repetitions. Lastly, an estimate of the original model performance will be computed by taking the apparent performance of the original model and subtracting the average optimism.

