### Model performance measures

To assess model performance, we will use the area under the Receiver Operating Characteristic (ROC) curve (i.e., AUC) and calibration slope to evaluate the discrimination and calibration of the models, respectively. Other overall performance measures that will be computed include the Scaled Brier score and Nagelkerke’s  $R^2$ . Decile calibration plots will also be generated for the final prediction models to further assess calibration, with Loess-smoothed calibration curves created for each imputed dataset. Additionally, a decision curve analysis will be performed on the final prediction models.

Based on the final validated logistic regression models, a points system will be developed to approximate the contribution of the risk factors in the estimate of risk of having a severe rebound to increase clinical utility of the models. (27)

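### The shrinkage row is labelled for a Cox-Snell R-squared of at least 0.1, but its printed n of 716.234 is the result for 0.2; at 0.1 the requirement is 1,528.2, above the estimated 1,270

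*Combined protocol and SAP*

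**What the plan says.** The Sample size section opens with "Calculations based on estimated sample size of 1270, and event rate of 50" per cent, then tabulates four criteria for developing a prediction model with a binary outcome. The Figure 3 block (Criteria i) sets a shrinkage factor of 0.9, is labelled "Rsquared CS (proportion of variation explained) at least .1", and prints a total n of 716.234. The note beneath it reads "Rsq often .1-.2 for binary for medical". The summary table repeats 716.234 against "Target a shrinkage factor of 0.9".

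The only R-squared printed as a numerical input is in the Figure 5 block (Criteria ii), where "Anticipated Rsq" is 0.2. The parameter count of 18 is printed in the Figure 2 block. The other requirements are 384.16 (margin of error), 1,013.2 (mean absolute prediction error, MAPE) and 420.427 (optimism in R-squared).

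**The concern.** A sample-size figure should follow from the assumption printed beside it, and this one does not appear to. For a fixed shrinkage target, the required n falls as R-squared rises. A row that promises the target for any R-squared from 0.1 upward must therefore be calculated at 0.1, its least favourable value.

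What is at stake is the section's implied conclusion. If R-squared is 0.2, MAPE sets the requirement and 1,270 exceeds all four figures. If it is 0.1, shrinkage sets the requirement and 1,270 falls short. A reader who trusts the label would also conclude that 716 patients hold overfitting to 10% at an R-squared of 0.1, which is not so.

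The point also touches the end product. The bootstrap estimates performance by "taking the apparent performance of the original model and subtracting the average optimism", which corrects the reported measures. Later, "a points system will be developed to approximate the contribution of the risk factors", and nothing in the plan says that the coefficients behind those points will be shrunk.

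**Working it through.** **Inputs.** Shrinkage factor S = 0.9 and the R-squared label come from the Figure 3 block. P = 18 comes from the Figure 2 block, the anticipated R-squared of 0.2 from the Figure 5 block, and the event rate of 50% and n = 1,270 from the opening line.

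**Does P = 18 fit the model?** Under Lower Limb Candidate Predictors and Model building, surgery type has nine groups (8 parameters), admission 1, sex 1, local anesthetic type 1, dexamethasone 1, and intraoperative anesthesia three levels (2). Age "will be modelled with a natural cubic spline (with 3 interior knots"), which takes 4. Total: 8 + 1 + 1 + 1 + 1 + 2 + 4 = 18.

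**Formula for Criteria i** (R² on the Cox-Snell scale):

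n = P / [(S − 1) × ln(1 − R²/S)]

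**Reproducing the printed figure.** With R² = 0.2: n = 18 / [−0.1 × ln(1 − 0.2/0.9)] = 716.234, equal to the printed value to three decimals. Solving back from 716.234 with P = 18 and S = 0.9 gives R² = 0.2000.

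**Using the label.** With R² = 0.1: n = 18 / [−0.1 × ln(1 − 0.1/0.9)] = 1,528.23. This exceeds 1,270 by 1,528.2 − 1,270 = 258.2.

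**Are the formula and P the plan's own?** The other three rows reproduce:

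- Margin of error: (1.96/0.05)² × 0.25 = 384.16.
- MAPE: exp[(−0.508 + 0.259 ln 0.5 + 0.504 ln 18 − ln 0.05)/0.544] = 1,013.20.
- Criteria ii: S = 0.2/(0.2 + 0.05 × 0.75) = 0.84211; the formula above with P = 18 and R² = 0.2 then gives 420.427. At R² = 0.1 this row would be 446.2, so it is barely affected.

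**Can another reading rescue the label?** To obtain 716.234 at R² = 0.1, P would have to be 8.44, or S would have to be 0.809; the plan states neither. Reading 0.1 as a Nagelkerke value (Cox-Snell 0.1 × 0.75 = 0.075) gives 2,068.7, which is further away.

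**Across the plan's own R-squared range** (P = 18; the last column solves the formula for S at n = 1,270):

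| Cox-Snell R² | n needed for S = 0.9 | Expected S at n = 1,270 |
|---|---|---|
| 0.10 | 1,528.2 | 0.882 |
| 0.15 | 987.3 | 0.920 |
| 0.20 | 716.2 | 0.941 |

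**Thresholds.** The smallest R² at which 1,270 meets S = 0.9 is 0.9 × [1 − exp(−18/(0.1 × 1,270))] = 0.1189. Shrinkage overtakes MAPE as the largest requirement when R² falls below 0.9 × [1 − exp(−18/(0.1 × 1,013.2))] = 0.1465. At n = 716.234 and R² = 0.1, the expected shrinkage factor is 0.809.

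**The case against.** The best defence is that the label is loose and the arithmetic is sound. The figure is exact for 0.2, the Figure 5 block prints 0.2 as its input, and a single anticipated value explains both rows that depend on R-squared. Literally, 0.2 also satisfies a condition of at least 0.1. The section refers to a Figure 4 and a spreadsheet that are not in the text available here, and the input for this row may be recorded there. So the absence of a printed R-squared in the row should not itself count against the plan.

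On consequences, the cohort is retrospective with fixed dates, so 1,270 is what is available and was not derived from this row. The table already asks for 1,013.2, so nobody proposes to stop at 716. The target is met over most of the plan's 0.1 to 0.2 range, and the bootstrap will estimate the actual overfitting whatever R-squared was assumed.

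Much of this stands. A loose label is plausible, the effect is modest, and no analysis changes. It does not remove the contradiction, because a floor of 0.1 has to be sized at 0.1. If 0.2 was meant, the plan used the favourable end of its own range without saying why. Shrinking the coefficients is a separate modelling choice that could be raised whatever the label said, so it is offered below only as an option.

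**Conclusion.** The concern holds. The shrinkage figure, in both places where it appears, does not follow from the R-squared stated beside it: 716.234 belongs to 0.2, and 0.1 requires 1,528.2. Correcting this changes whether 1,270 is shown to satisfy one of the four criteria.

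The practical size is small. At worst within the plan's own range, the expected shrinkage factor at 1,270 is 0.882 against a target of 0.9, a miss of 0.018. From an R-squared of about 0.119 upward there is no miss.

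This rests on the 18 parameters printed in the Figure 2 block also applying to the shrinkage row. The predictor list and the exact match at 0.2 both support that. It also takes the estimated 1,270 as the number analysed. The documents do not establish whether the label or the figure is the slip.

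**What to change.** Reconcile the label and the figure in the Figure 3 block and in the summary table, in one of two ways:

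- keep the label and print 1,528.2 for an R-squared of 0.1; or
- relabel the row as 0.2, justify that value for this outcome, and show the 0.1 result beside it.

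In either case add one sentence:

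> With 18 parameters, n = 1,270 meets the 0.9 target only if Cox-Snell R-squared is at least about 0.119; the expected shrinkage factor is about 0.88 at 0.1, 0.92 at 0.15 and 0.94 at 0.2.

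Optionally, apply the bootstrap-estimated calibration slope as a uniform shrinkage factor to the final coefficients and re-estimate the intercept before building the points system. The planned bootstrap already produces that slope.

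The required change is to SAP wording only. Its one drawback is that the stated position becomes less favourable. No additional patients are needed.
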